**Purpose of the Study:**

To determine whether hyperpolarized 129Xenon MRI can detect improvements in pulmonary gas exchange in patients with PH treated with iTRE. We will associate this with changes in serum concentrations of treprostinil and levels of peripheral vasodilation.

**Background & Significance:**

Pulmonary hypertension (PAH) carries a significant economic burden, with average annual health care costs of ~ \$100,000/yr. The diagnosis of PAH can be challenging, as it requires fulfillment of specific clinical and hemodynamic criteria. However, these are limited because they do not allow the diagnosis of PAH in the setting of concomitant left heart disease or lung disease. Patients with mild to moderate idiopathic pulmonary fibrosis (IPF) or chronic obstructive pulmonary disease (COPD), which are common in older patients, technically cannot be diagnosed with true PAH, but are diagnosed with Pulmonary Hypertension (PH). Similarly, hemodynamic criteria are limited by arbitrary cutoffs for mean pulmonary artery pressure (mPAP), pulmonary capillary wedge pressure (PCWP), and pulmonary vascular resistance (PVR) obtained at right heart catheterization (RHC) (PH is defined as mPAP  $\geq$  25 mmHg; PAH is defined as mPAP  $\geq$  25-mmHg and a PCWP  $\leq$  15 mmHg, with some criteria recommending an additional cutoff of PVR  $\geq$  3 Woods units. Moreover, it is currently unclear what constitutes abnormal hemodynamics in the setting of in lung disease, which can increase the PVR. These hemodynamic criteria also frequently exclude patients who may have a borderline elevation in mPAP or abnormalities primarily associated with exercise that are not captured with a resting heart catheterization. As the majority of patients who are now evaluated for PAH are older with common cardiac and pulmonary comorbidities, the clinical and hemodynamic criteria are frequently inadequate for diagnosing patients who actually have PVD.

If successful, Xe MRI could overcome the current limitations of PVD diagnosis while conferring a number of potential benefits. First, imaging the abnormalities in the lungs allows the diagnosis of PVD in the setting of concomitant heart or lung disease. With HP Xe MRI, abnormalities in gas exchange secondary to PVD can be directly visualized. Second, non-invasive diagnosis of PVD could remove the need for an invasive RHC. While RHC is a relatively safe procedure, there are a number of limitations to the interpretation of RHC, including arbitrary cutoffs for mPAP, PCWP, and PVR. Third, the abnormalities on HP Xe MRI could be used to non-invasively monitor response to therapy. If we are successful in demonstrating the applicability of HP Xe MRI, this technology holds the promise of greatly improving the diagnosis and management of PVD.

### **Design & Procedures:**

This study will consent 15 patients (accrued 12 subjects total) with pulmonary hypertension (PH). Patients will be on inhaled treprostinil (iTRE) as standard of care for their PH. Inhaled treprostinil (iTRE) is an FDA approved medication under the brand name of Tyvaso. The major pharmacologic actions of treprostinil are direct vasodilation of pulmonary and systemic arterial vascular beds and inhibition of platelet aggregation. The medication is delivered noninvasively, directly to the lungs using the approved ultrasonic nebulizer delivery system. Patients will take the inhaled treatment four times a day, about every four hours.

Patients will be characterized by their Xe MRI imaging, peripheral vasodilation and serum treprostinil concentration before and after treatment with iTRE. As iTRE has a plasma concentration half-life of ~ 45 minutes and time-to-peak concentration of 15 minutes, imaging will be conducted immediately before, 15 minutes after and 2-4 hours after drug treatment. This would potentially allow the visualization of changes in gas diffusion and peripheral vasodilation associated with iTRE. This is similar to changes seen in ventilation in asthma after treatment with bronchodilators. A follow-up scan at the 2-4hr time point would also allow us to test whether vasodilation persists in the lung vasculature compared to the peripheral circulation. This study seeks to deploy several forms of Xe MRI contrast. Specifically, the Xe MRI scans will provide 3D images of ventilation and gas exchange, and spectroscopic indices will be evaluated to test gas exchange dynamics with high temporal resolution. This will be augmented with several conventional H MRI scans to delineate the subject's thoracic cavity.

Once the subjects has signed consent, the study session will begin with a collection of relevant patient history and symptoms, measurement of hemoglobin levels (finger sensor), and urine pregnancy testing (if applicable). Study team will use the PFTs that are available from the medical record. Subjects will receive an IV catheter to be used for blood draws. The following activities will take place for the MRI procedure:

1. Patient receives first scan before scheduled dose of iTRE (trough study) Baseline timepoint: Xe calibration and dissolved-phase spectroscopy - to obtain global RBC:barrier ratios, RBC oxygenation shifts, and spectral linewidths; Isotropic 3D Xe gas exchange MRI – to detect focal defects in gas transfer from airspaces to RBCs in capillary bed; Other H scans to obtain anatomic data on the lung.
2. Assessment of peripheral vasodilation in the arm and hands with noninvasive laser speckle imaging
3. Blood sample for serum treprostinil concentration
4. Subject takes iTRE treatment as with standard of care. Timepoint 1: Wait ~ 15 minutes to peak effect (peak study). Patient receives second scan: Xe calibration and dissolved-phase spectroscopy - to obtain global RBC:barrier ratios, RBC oxygenation shifts, and spectral linewidths; Isotropic 3D Xe gas exchange MRI – to detect focal defects in gas transfer from airspaces to RBCs in capillary bed; Other H scans to obtain anatomic data on the lung.

5. Assessment of peripheral vasodilation in the arm and hands with noninvasive laser speckle imaging
6. Blood sample for serum treprostinil concentration
7. Timepoint 2: 2-4 hrs after initial treatment with iTRE; Patient receives third scan:  $^{129}\text{Xe}$  calibration and dissolved-phase spectroscopy - to obtain global RBC:barrier ratios, RBC oxygenation shifts, and spectral linewidths; Isotropic 3D  $^{129}\text{Xe}$  gas exchange MRI – to detect focal defects in gas transfer from airspaces to RBCs in capillary bed; Other  $^1\text{H}$  scans to obtain anatomic data on the lung.
8. Assessment of peripheral vasodilation in the arm and hands with noninvasive laser speckle imaging
9. Blood sample for serum treprostinil concentration

With each time point (baseline/trough scan, timepoint 1 scan, timepoint 2 scan) the patient will undergo several scans after inhalation of HP  $^{129}\text{Xe}$  gas. Each dose will be limited to a volume less than 25% of subject lung capacity (TLC) as is the case for all protocols currently carried out under IND 109,490. After each  $^{129}\text{Xe}$  dose, the table will be moved out of the magnet bore and the subject queried for any symptoms. The next  $^{129}\text{Xe}$  dose and scan will be administered when the subject and study personnel are ready. Subjects will undergo a  $^{129}\text{Xe}$  MR spectroscopy calibration scan,  $^{129}\text{Xe}$  ventilation MRI, and  $^{129}\text{Xe}$  gas exchange MRI. Any given  $^{129}\text{Xe}$  MRI scan may be repeated, if necessary. There is no limit to the number of  $^{129}\text{Xe}$  scans allowed during the session, although current  $^{129}\text{Xe}$  production capabilities generally limit this to 5  $^{129}\text{Xe}$  doses.

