### **Data Analysis & Statistical Considerations:**

We will perform pairwise comparisons for all endpoints before and after treatment with iTRE with correction for multiple comparisons. We will also compare the baseline and post-treatment values to a group of normal subjects so we can assess the degree of normalization of gas transfer associated with drug treatment.

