### **Statistical Plan**

We will perform pairwise comparisons for all endpoints before and after treatment with Tyvaso with correction for multiple comparisons. We will also compare the baseline and post-treatment values to a group of normal subjects so we can assess the degree of normalization of gas transfer associated with drug treatment.

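### The plan states a lung-versus-periphery persistence question but no planned test answers it; prespecify one within-patient contrast and note the previous-dose time

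*Combined protocol and SAP*

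**What the plan says.** Design & Procedures gives the reason for the third imaging session: it "would also allow us to test whether vasodilation persists in the lung vasculature compared to the peripheral circulation". The late measurement is step 7 of the MRI procedure: "Timepoint 2: 2-4 hrs after initial treatment with iTRE; Patient receives third scan". Laser speckle imaging of the arm and hands and a blood sample accompany every scan.

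The analysis is stated twice, in nearly the same words. Data Analysis & Statistical Considerations has "We will perform pairwise comparisons for all endpoints before and after treatment with iTRE with correction for multiple comparisons"; Statistical Plan has "We will perform pairwise comparisons for all endpoints before and after treatment with Tyvaso with correction for multiple comparisons". Each adds a comparison of baseline and post-treatment values with normal subjects. Purpose of the Study adds an association: "We will associate this with changes in serum concentrations of treprostinil and levels of peripheral vasodilation".

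On the baseline, step 1 reads "Patient receives first scan before scheduled dose of iTRE (trough study) Baseline timepoint". Selection of Subjects requires stable maintenance iTRE, and Design & Procedures says "Patients will take the inhaled treatment four times a day, about every four hours". Baseline also includes "Blood sample for serum treprostinil concentration" (step 3). The session opens with a general history. The time of the previous iTRE treatment is not named among the items collected, and the dose of the day to be studied is not fixed. Privacy, Data Storage & Confidentiality links each image to the date and time of its MRI.

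**The concern.** The persistence question is comparative: does the lung keep its response longer than the periphery? The planned analyses ask other things. A before/after test asks whether one endpoint changed in one bed. The comparison with normal subjects asks how far gas transfer normalises. A correlation between lung change and peripheral change can be high or low whether or not one bed holds its response longer.

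Without a named contrast, the natural fallback is to set a significant late lung result beside a non-significant late peripheral one. That pattern does not show a difference between the beds.

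A second issue bears on the late lung result alone. Baseline is measured in patients already taking the drug. If some vascular effect of the previous dose is still present at baseline, subtracting it takes away part of the persistence that the late scan is meant to show. A flat late-minus-baseline result could then mean no persistence, or an effect already present at baseline.

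**Working it through.** The documents give no alpha, effect size, SD or duration of vascular effect, so there is no stated figure to reproduce. Inputs from the documents are 12 accrued subjects, four doses a day about 4 h apart, a late scan at 2-4 h, and a plasma half-life of about 45 min with peak at 15 min. Everything else below is assumed and shown as a range.

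**1. Two separate tests when persistence is equal.** Simulation: 12 patients, the same true late change in each bed (0.3 to 1.2 SD of change), correlation 0.3 or 0.6 between beds, paired t-tests at two-sided 0.05 or 0.05/6 = 0.0083, 40,000 runs per setting. Share of runs in which exactly one test is significant:

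| True change (SD) | r=0.3, alpha 0.05 | r=0.6, alpha 0.05 | r=0.3, alpha 0.0083 |
|---|---|---|---|
| 0.3 | 23% | 18% | 7% |
| 0.6 | 41% | 31% | 27% |
| 0.9 | 26% | 20% | 43% |
| 1.2 | 6% | 5% | 28% |

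Across all settings the range is about 5% to 43%.

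**2. Why the contrast should be relative to each bed's peak.** Suppose both beds retain 40%, with peak changes of 2 and 1 SD. The late changes are 0.8 and 0.4 SD, so a contrast of late changes sees a difference of 0.4 although persistence is equal; it rejects in 19-29% of trials, and a relative contrast in 2.5-2.7%. Conversely, if the lung retains 60% of 1 SD and the periphery 30% of 2 SD, both late changes are 0.6 SD. The late-change contrast then rejects at 5%, and the relative contrast at 15-25%.

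**3. Precision at n=12.**
- Difference in standardised late change: 95% half-width = t(0.975, 11) × √(2−2r)/√12, with t = 2.201. For r=0.3 this is 2.201 × 1.183/3.464 = 0.75 SD; for r=0.6 it is 2.201 × 0.894/3.464 = 0.57 SD.
- Difference in retained fraction f (delta method on ratios of group means): half-width = 2.201 × √{A(1/p₁² + 1/p₂² − 2b/(p₁p₂))/12}, where A = 1 + f² − 2fw, p is the peak change in SD, w the peak-late correlation within a bed and b the correlation between beds (cross-bed peak-late correlation taken as b×w). With f=0.4 and both peaks 1 SD, w=0.5 and b=0.3 give A=0.76 and a half-width of 0.66; w=0.6 and b=0.6 give A=0.68 and 0.47. That is roughly 0.5-0.7 over nearby assumptions. Both peaks at 2 SD halve it to 0.23-0.33. If one peak is only 0.5 SD, it is about 1.

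**4. The trough baseline.** Model: each dose adds an effect 2^(−t/h), with doses at 0, 4, 8 and 12 h each day and therefore a 12 h overnight gap. Contrast = effect at (study dose + t) minus effect just before the study dose. Share captured = contrast ÷ 2^(−t/h).

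| Effect half-life h | True residual at 2 h | Captured at 2 h, dose 1/2/3 | True residual at 4 h | Captured at 4 h, dose 1/2/3 |
|---|---|---|---|---|
| 0.75 h (plasma) | 0.157 | 100/87/86% | 0.025 | 100/2/0% |
| 2 h | 0.500 | 98/74/69% | 0.250 | 94/23/6% |
| 4 h | 0.707 | 90/74/66% | 0.500 | 76/38/19% |
| 8 h | 0.841 | 80/73/67% | 0.707 | 57/40/29% |
| 16 h | 0.917 | 74/70/67% | 0.841 | 45/38/32% |

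Example: h=4 h, third dose, 4 h scan gives 0.095/0.500 = 19%. At the plasma half-life the shares at 4 h look poor, but the absolute loss is at most 0.025, or 2.5% of peak. The trough-to-peak contrast keeps 96-98% at second- and third-dose visits for half-lives of 2-8 h.

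A variant with decay starting from a 15-min peak and one previous dose 4 h earlier shows the same pattern: at a 3 h half-life it loses 23% at 2 h and 60% at 4 h.

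A relative contrast does not cure this. At h=4 h with a 4 h scan, the true retained fraction is 2^(−3.75/4) = 0.52. The observed values are 0.381/0.948 = 0.40, 0.190/0.931 = 0.20 and 0.095/0.923 = 0.10 for doses 1, 2 and 3.

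**The case against.** Several counter-arguments have force.

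- **The baseline issue is conditional.** The only half-life in the documents is the plasma one, and at that value almost nothing is lost in absolute terms. Large losses need a longer lung effect, a second- or third-dose visit and a scan near 4 h. This stands, and it is why the point is only supporting. But an effect that outlasts plasma is what the persistence question is about.
- **A safeguard exists.** Trough serum level indexes residual drug: in the 15-min-peak model it is 3.1% of peak 4 h after a dose and 0.002% after 12 h. Scan times are already captured, and the study-dose time can be approximated from the peak scan, about 15 minutes after treatment. This stands in part: serum does not show a vascular effect that outlasts the drug in plasma.
- **The misreading is hypothetical.** The plan does not say that one significant and one non-significant result will be taken as differential persistence. True; the 5-43% shows only that the fallback is unreliable.
- **The contrast will be imprecise.** Also true. That favours reporting an interval over comparing two p-values.

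A reader might infer more than the documents support. They do not show that the previous-dose time goes unrecorded: they do not name it, and the opening history could capture it. Nor must a 4 h contrast vanish whatever the effect duration. That needs regular 4 h dosing round the clock, whereas four daily doses leave an overnight gap, and 19-40% is captured at second- and third-dose visits for half-lives of 4-16 h. A 2-4 h scan also fits within an interval of about 4 h, so the dosing description and the imaging window do not contradict each other.

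**Conclusion.** The gap between question and analysis holds on the text alone: a between-bed persistence question is stated, and no planned comparison tests it. The 5-43% discordance rests on the assumed effects, correlations and alpha levels.

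The baseline point holds only conditionally. If the previous dose was about 4 h earlier and the lung effect has an assumed half-life of 2-16 h, late-minus-baseline at second- or third-dose visits captures about 66-74% of the study dose's residual at 2 h and 6-40% at 4 h. First-dose visits capture 76-98% at half-lives of 2-4 h, and less if the effect lasts longer. A positive late lung result would still be evidence of persistence; a flat one is ambiguous.

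The matter is confined to a secondary question. A reader might infer that the main before/after result is compromised, but the trough-to-peak comparison is almost unaffected. This is a cheap improvement, not a flaw in the study's central aim.

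**What to change.** 1. Prespecify one within-patient lung-versus-periphery contrast at 2-4 h, using one named lung endpoint and one named laser-speckle endpoint. Express the peak-to-late change relative to each bed's own peak response. Give a confidence interval, state the contrast's place in the multiplicity correction, and report it as an exploratory estimate.
2. Name the time of the previous iTRE treatment as an item in the opening history. Use it, with the trough serum level and the scan times already held, in a sensitivity analysis. With 12 patients, enter such covariates one at a time.
3. State that a non-significant late-minus-baseline lung result will not be read as absence of persistence.

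The cost is one extra recorded time and a little more analysis, with no change to dosing or visit booking. The drawback is the low precision shown above, and the relative contrast does not itself remove the baseline problem, so item 2 is still needed.

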### **Selection of Subjects:**

We propose to recruit and consent 15 subjects (accrued 12 subjects total) with known PH on treatment with iTRE that are followed in the Duke Pulmonary Vascular Disease Clinic. Inclusion criteria includes: PH (mPAP  $\geq 25$  mmHg, PCWP  $\leq 15$  mmHg in the absence of significant concomitant left heart disease or lung disease), , maintenance on a stable, well-tolerated treatment dose of iTRE (ideally  $\geq 8$  breaths QID). Pregnant women will be excluded from this study. Women of childbearing potential must have a negative urine pregnancy test in order to participate on this study.

Definition of Women of CBP: The median age of menopause in the US, defined as 12 months of amenorrhea, is 51 years; by age 48, approximately 15% of women will be postmenopausal, while virtually 100% will be post-menopausal by age 55. Women are considered past the age of “child-bearing potential” if they are greater than 55 years of age, OR they are at least 50 years of age AND o have not menstruated for at least 12 months, OR have a documented Follicle Stimulating Hormone (FSH) level of greater than 40 mIU/mL. they are at least 45 years of age AND o have not menstruated for at least 18 months, OR o have a documented Follicle Stimulating Hormone (FSH) level of greater than 40 mIU/mL. For drugs classified, or likely to be classified, as FDA Category X, the duration of amenorrhea for women of all ages must be 24 months, consistent with FDA labeling of these drugs.

### **Subject Recruitment and Compensation:**

Patients will be recruited based on predetermined inclusion criteria. They will be recruited in the Pulmonary Vascular disease clinics and inpatient services at Duke by their care providers. The patient's provider will initiate conversation with the subject about the research trial and assess their interest in participation. The screening of subjects will be conducted by the study coordinator and will include the informed consent process.

Before entry into the protocol, the nature and risks of the study will be reviewed with each subject. Each subject will be given the opportunity to read the consent form and ask questions. After all questions by the study subject are answered, and before any protocol specified procedures are initiated, each subject will sign and date the consent form. A copy of the signed consent will be provided to the subject.

[name] is founder and chief technology officer of Polarean, Inc. a start-up company that seeks to commercialize hyperpolarized  $^{129}\text{Xe}$  gas MRI technology. He is a shareholder in the company and provides it with technical consulting. In addition, Polarean has licensed from Duke, a patent on which [name] is an inventor, and is currently evaluating several others. For these reasons he has had a conflict management plan, administered by the Duke Office of Research Integrity. The study proposed here uses Polarean technology, but is not sponsored by the company nor is it being used for regulatory advancement with FDA. However, if the findings are positive, Polarean may have an interest in commercializing these aspects of the technology as well. Therefore, consistent with his management plan, [name] will not serve as principal investigator on this study, nor will he obtain consent from subjects. He will oversee the technical aspects of hyperpolarized gas production and MR image acquisition. However, data analysis will be overseen by [name], who also serves as overall principal investigator on this protocol. Duke is being paid to conduct the study by United Therapeutics. Subjects will take their standard of care iTRE medications during the necessary timepoints in the study. Subjects will receive \$150 for their time and travel expenses.

### **Consent Process:**

See Section 14 of the e-IRB submission form and complete the questions in that section.

### **Subject's Capacity to Give Legally Effective Consent:**

Subjects without capacity to give consent will not be recruited into this study.

### **Risk/Benefit Assessment:**

#### **Potential Risks**

The risks of participating in this study are considered greater than minimal risk. MRI is a non-invasive imaging modality that involves no ionizing radiation. All subjects will have already completed a standard questionnaire to screen for contraindications to MRI imaging since the parent trial also employs MR imaging.

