### **Risks of Incidental Findings**

Since the MRI methods being tested are experimental, the MRI images will not be formally reviewed for incidental findings. However, if there is something that is of concern to the PI, then the PI will approach the IRB for guidance on how to proceed on a case-by-case basis. The consent will clearly state that the MRI images will not be evaluated for incidental imaging findings.

**Protection Against Risk:** Study visits and informed consent will be performed in private rooms, to prevent potential loss of confidentiality. This individual will be present in the MRI suite during 129Xe administration and will monitor all aspects of the subject's wellbeing and record any transient CNS effects and adverse events should they occur. The subject will be monitored continuously by an MRI-compatible pulse oximeter, recording both heart rate and oxygen saturation. Subjects may discontinue the study at any time. The MRI suite is also equipped with a safe source of supplemental oxygen that can be provided if needed for patients with pulmonary disease to maintain O2 saturation. All subjects will receive a 24-hour follow-up phone call to check for any symptoms or adverse effects. Any symptoms or effects will be recorded, regardless of their suspected association with 129Xe MRI.

Extraordinary care will be taken to ensure that all patient data remains confidential and any information is deidentified prior to publication or presentation. All study personnel will have completed their institution's mandatory training in human subjects' research and protecting PHI.

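### MRI-contraindication screening is promised as already done because of an unidentified parent trial that recruitment does not require, and this study's own pre-scan steps do not list it

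*Combined protocol and SAP*

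**What the plan says.** The Potential Risks text, under Risk/Benefit Assessment, rates the study as greater than minimal risk. It then deals with MRI safety screening in one sentence: "All subjects will have already completed a standard questionnaire to screen for contraindications to MRI imaging since the parent trial also employs MR imaging".

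Three other sections bear on this.

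- **Selection of Subjects** describes patients "with known PH on treatment with iTRE that are followed in the Duke Pulmonary Vascular Disease Clinic". It adds hemodynamic criteria and a stable treatment dose. The exclusion it states is pregnancy: "Pregnant women will be excluded from this study". It mentions neither a parent trial nor an MRI contraindication.
- **Subject Recruitment and Compensation** gives the route in: "They will be recruited in the Pulmonary Vascular disease clinics and inpatient services at Duke by their care providers". The study coordinator does the screening. Its content is described only as including informed consent, and "before any protocol specified procedures are initiated, each subject will sign and date the consent form".
- **Design & Procedures** sets the order of the session: "Once the subjects has signed consent, the study session will begin with a collection of relevant patient history and symptoms". Hemoglobin by finger sensor and, where applicable, a urine pregnancy test follow. Lung function results come from the medical record, and an IV catheter is placed. The first numbered item of the MRI procedure is then the baseline scan.

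**The concern.** The risk section treats the contraindication check as finished before a subject reaches this study, and it rests that on the subject having been in another trial that used MRI. The selection and recruitment sections describe a study that patients enter directly from routine care. A patient can meet every stated entry criterion without ever having had a research MRI. For that patient, the reason given for regarding the questionnaire as complete does not apply.

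What is at stake is a safety assurance, not an estimate. Staff who follow the text are told that the form has been done. Nothing in the listed session steps asks them to complete it or to confirm an earlier completion.

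**Working it through.** There is no figure to reproduce and no statistical calculation applies. The check consists of setting the sections side by side.

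**Step 1: what the risk sentence depends on.** It makes a universal claim (all subjects) in a completed tense, and gives one reason (the parent trial also used MRI). That reason covers all subjects only if every subject has been in the parent trial.

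**Step 2: whether the protocol makes that so.** Nothing in Selection of Subjects or in Subject Recruitment and Compensation requires membership of another trial. Across the visible text, a parent trial is mentioned once, in the risk sentence itself.

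**Step 3: whether another study mentioned could be the parent.** The nearest candidate is the existing protocol in Background & Significance. It is described as preliminary work in two patients with suspected pulmonary vascular disease who did not meet strict criteria for pulmonary arterial hypertension. It is not presented as the source of this study's subjects, whose entry criteria are mPAP of at least 25 mmHg and PCWP of at most 15 mmHg.

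**Step 4: whether this study's own steps include the check.**

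| Stage | What the text lists | Questionnaire named? |
|---|---|---|
| Entry criteria (Selection of Subjects) | Hemodynamics, stable treatment, pregnancy exclusion | No |
| Screening (Subject Recruitment and Compensation) | Coordinator screening, including consent | No |
| Session start (Design & Procedures) | History and symptoms, hemoglobin, pregnancy test, lung function from the record, IV catheter | No |
| MRI procedure, item 1 | Baseline scan | No |
| Risk text (Potential Risks) | Questionnaire, as already completed | Yes |

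The check is promised in the risk text and is absent from the procedural text. The pregnancy test, also a pre-scan safety check, appears both in the entry criteria and in the session steps.

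**Step 5: scope.** The unit is the person, because one questionnaire serves one subject. With 12 accrued and 15 consented, that is 12 × 1 = 12 to 15 × 1 = 15 forms.

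**The case against.** The strongest reply is that the commitment already exists. The risk sentence covers every subject and places the check before any scan in this study. That stands. A reader might infer that the protocol promises no MRI safety check before the first scan, but the documents do not support this. What is missing is a procedural step and a reason that fits the recruitment route.

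A second reply is that this is an undefined reference and not a contradiction. Being recruited in clinic is compatible with having been in an earlier MRI study, and no section says that subjects are new to MRI. This also stands in part. A reader might infer that no parent trial exists, and the text does not show that. But even if one exists, the entry criteria as written do not limit the study to its participants, so the words about all subjects still lack support.

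A third reply is that the check may sit in text that is not visible or not detailed. The title and consent pages were removed before review, and the Consent Process section points to a separate e-IRB form. The patient history taken at the session, or the coordinator's screening, could include MRI safety questions, since neither list is closed. This is a fair limit. A reader might infer that some subjects would be scanned unscreened, and the documents do not support that either. Failing to find the questionnaire in the procedural sections shows where the form is named. It does not demonstrate a gap in screening.

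**Conclusion.** The point holds as an inconsistency between a safety assurance and the recruitment text. The risk section gives a single reason for treating the MRI questionnaire as complete, and the entry and recruitment sections do not make that reason true for every subject. For a subject with no earlier research MRI, following the visible text as written means that no listed step in this study completes or confirms the only visible MRI-contraindication check.

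It is worth fixing because it concerns safety and the repair is small. It affects at most the 15 people consented, is not evidence of harm, and has no bearing on any endpoint, comparison, error rate or power. The conclusion rests on the visible text alone. A parent trial identified in the removed or referenced material would settle what the sentence refers to, but the sentence would still have to be reconciled with the entry criteria.

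**What to change.** Reconcile the Potential Risks sentence with Design & Procedures, Selection of Subjects, and Subject Recruitment and Compensation.

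1. Replace the parent-trial sentence. The new sentence should say that the standard MRI-contraindication questionnaire already named there is completed under this protocol for every subject, or a prior completion confirmed, after consent and before the first scan. Placing it after consent agrees with the rule that consent precedes any protocol procedure.
2. Add the questionnaire as one item in the pre-scan steps of Design & Procedures.
3. If a parent trial does exist, identify it. The first two changes work whether or not it exists, and they do not require enrolment in it to become an entry condition.

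The cost is one replaced sentence, one added item, and one short form for each of 12 to 15 subjects. The documents give no time per form; a few minutes each is an assumption. No extra visit is needed.
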